6.2.1. Pharmacokinetic Samples

Plasma samples for GS-5829 PK will be collected (\pm 10 minutes) in cohorts 1-3 of Group 1 on Study Day 1 at pre-dose (0 hr), 0.5, 1, 2, 3, 4, 6, 8, 12, and 24 hours post-dose and in cohorts 4-8 of Group 1 and all cohorts of Group 2 on Cycle 1 Day 1 at pre-dose (0 hr), 0.5, 1, 2, 3, 4, 6, 8, 12, and 24 hours post-dose. Additional samples will be collected at 48 and 72 hours post-dose in dose levels 1 – 3 of Group 1 relative to first dose of GS-5829. Plasma samples for GS-5829 PK will be collected in all cohorts (Group 1 and Group 2) at pre-dose (0 hr), 0.5, 1, 2, 3, 4, 6, 8, 12, and 24 hours post-dose relative to GS-5829 administration on Cycle 1 Day 8. Sparse PK samples will be collected in all cohorts (Group 1 and Group 2) at trough (20-26 hours post-dose) on Cycle 1 Day 4, 2 - 4 hours post-dose on Cycle 1 Day 15, and anytime post-dose on Day 1 of Cycles 2 through 6.

At one or more dose levels, PK samples will be collected on Day 1 of Cycle 2 at pre-dose (0 hr) and 0.5, 1, 2, 3, 4, 6, 8, and 24 hours post-dose. GS-5829 dose will be administered in fed state on Day 1 of Cycle 2.

Urine will be collected for GS-5829 PK in Group 1 cohorts 1-3 on Study Day 1 and in Group 1 cohorts 4-8 on Cycle 1 Day 1 at pre-dose, 0-6 hours, 6-12 hours, and 12-24 hours post-dose relative to first dose of GS-5829.

Subjects in the Group 3 lymphoma expansion will have PK drawn at pre-dose, 1, 2, 4, 6, and 24 hours post-dose on Cycle 1, Day 8. PK samples will also be drawn at pre-dose on Day 1 of Cycles 2, 4, and 6.

Plasma and urine concentrations of GS-5829 will be determined and PK evaluated. Plasma and urine concentrations of GS-5829 metabolite(s) may be determined and PK explored. Unbound concentrations of GS-5829 and/or metabolites may be determined. Plasma concentrations of fulvestrant, exemestane, or metabolites may be determined and PK explored.

CCI

[REDACTED]

[REDACTED]

[REDACTED]

[REDACTED]

CCI [Redacted]

[Redacted]

[Redacted]

[Redacted]

CCI [Redacted]

[Redacted]

[Redacted]

[figure not shown]
[Redacted]

[Redacted]

CCI [Redacted]

[Redacted]

CCI

6.3.4. Unscheduled Procedures

Unscheduled procedures, including, but not limited to, vital signs, 12-lead ECG, and CT or MRI, will be recorded on the applicable eCRFs.

6.4. Post-treatment Assessments

6.4.1. Post-Study Phone Call

Subjects will be contacted by phone 30 days (\pm 7 days) after the last dose of GS-5829 to assess for AEs. For subjects who come off study for reasons other than disease progression, the site should also obtain information post-study anti-cancer therapies, surgeries, and date of definitive disease progression (if known).

6.5. Criteria for Discontinuation of Study Treatment

See Sections 3.4 and 3.5 for discontinuation criteria.

6.6. Replacement of Subjects

If a subject is withdrawn from the study for any reason other than a DLT prior to completion of the DLT assessment window, a replacement subject will be enrolled at the same dose level as the replaced subject. To be evaluable for the DLT observation, a subject must receive at least 21 doses of GS-5829, complete all safety procedures through Day 28, or experience a DLT prior to Day 28.

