1	2 mg	25 mg orally once daily	500 mg intramuscularly day 1, 29 and then every 28 days**
2	3 mg		
3	4 mg		
4	6 mg		
5	9 mg		
6	12 mg		

* Dose Levels may be modified based on emerging safety and PK results.

** Subjects initiating fulvestrant on this study should receive a single additional dose of fulvestrant on Cycle 1 Day 15.

Group 2A and Group 2B will dose escalate independent of each other. In both Group 2A and Group 2B, each cohort will consist of 3 newly enrolled subjects who will be treated at the specified dose level. After all subjects in each cohort have been followed for at least 28 days after the first dose of GS-5829, a dose-DLT model (Bayesian logistic regression model) utilizing all available GS-5829 safety data will be built and will provide estimates of DLT rates at all dose levels. The dose-DLT model recommended dose for the next cohort will be the one having the highest chance that the DLT rate will fall in the target interval [16%, 33%) and a probability of <25% that the DLT rate exceeds 33%.

Group 3 Lymphoma expansion:

In addition to the minimum 6 subjects in Group 1 with solid tumors or lymphomas who will be enrolled to confirm the MTD, an additional minimum of 6 subjects with aggressive NHL (DLBCL or PTCL) may be enrolled at a dose no higher than the MTD and complete a 28 day safety period. If ≤ 1 of these 6 subjects reports a DLT within this 28 day safety period, then up to an additional 34 subjects may be enrolled to evaluate the efficacy and tolerability of GS-5829 in lymphoma (a maximum total of 40 subjects with lymphoma enrolled). A minimum of 20 DLBCL and 5 PTCL subjects will be enrolled into this group. If ≥ 2 of 6 subjects report a DLT, then an additional 6 subjects will be enrolled at a lower dose level, or at an alternative dosing schedule, which decreases the total amount of GS-5829 administered over a 28-day period to at least 25% less than the previous cohort (eg 14 days on and 7 days off).

The final dose escalation decisions will be made by the SRT, following a review of the model recommendation and all relevant data available including safety information, PK, CCI clinical data from evaluable patients.

Table 3-3. Group 3: Single agent expansion in aggressive lymphomas

Dose Level	GS-5829*	# of subjects enrolled initially	Total number of subjects
1	≤ MTD determined by Group 1	6 subjects	If no DLT in first 6 subjects expand to maximum total of 40 (approx. 34 additional subjects)

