-1	is ≥25% less total GS-5829 administered over a 28 day period	6 subjects	If no DLT in 6 subjects at this dose level, then expand to maximum total of all Group 3 subjects of 40 (approx. 28 additional subjects)

Sites in France will be limited to Group 3 enrollment only.

Dose escalation in Group 1 will continue until identification of the MTD, or a suitable lower recommended dose, for Phase II studies. At least 6 subjects should be treated and evaluated at the GS-5829 dose level recommended for Phase II studies.

A DLT in Group 1 or 2 is a toxicity defined below considered possibly related to GS-5829 occurring during the DLT assessment window (Study Day 1 through C1D28) in each cohort.

- Grade ≥ 4 neutropenia (absolute neutrophil count [ANC] < 500/mm³)
- Grade ≥ 3 neutropenia (ANC < 1000/mm³) with fever (a single temperature of > 38.3°C or a sustained temperature of ≥ 38°C for more than one hour)
- Grade ≥ 3 thrombocytopenia
- Grade ≥ 2 bleeding (e.g. gastrointestinal, respiratory, epistaxis, purpura)
- Grade ≥ 3 or higher non-hematologic toxicity, except:
 - Grade 3 nausea or emesis with maximum duration of 48 hours on adequate medical therapy
 - Grade 3 diarrhea which persists for < 72 hours in the absence of maximal medical therapy
- Grade ≥ 2 non-hematologic treatment-emergent adverse event (TEAE) that in the opinion of the investigator is of potential clinical significance such that further dose escalation would expose subjects to unacceptable risk
- Treatment interruption of ≥ 7 days due to unresolved toxicity
- For certain toxicities such as laboratory assessments without a clear clinical correlate, a discussion between the Investigator and Medical Monitor may take place to determine if

this AE should be assessed as a DLT necessitating dose reduction. However, any Grade 3 or Grade 4 elevation in AST or ALT associated with a Grade 2 elevation in bilirubin that is at least possibly related to study drug will be considered a DLT.

Group 3: For the first 6 subjects enrolled in the aggressive lymphoma group (Group 3), a modification of the DLT assessment for hematologic toxicity will be:

- Grade ≥ 4 neutropenia (absolute neutrophil count [ANC] $< 500/\text{mm}^3$) which persist for > 3 days upon interruption of GS-5829 (administration of growth factors not allowed concurrently, but allowed during GS-5829 interruption)
- Grade ≥ 4 thrombocytopenia ($< 25,000/\text{mm}^3$)

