3.3. Study Treatments

Subjects who meet eligibility criteria will receive GS-5829 orally once daily. Subjects in the first 3 cohorts will receive a single dose of GS-5829 and then approximately 7 days later start their first 28 day cycle of GS-5829 once daily. Each cycle will consist of 28 days. Safety and efficacy assessments will occur on an outpatient basis including assessment of tumor response, physical exam, vitals, electrocardiogram (ECG), collection of blood samples (for routine safety labs, GS-5829 PK, CCI [REDACTED] at applicable visits), urine pregnancy (every 4 weeks while receiving GS-5829 in females of childbearing potential), and assessment of AEs. In addition, subjects will undergo computed tomography (CT)/magnetic resonance imaging (MRI) or applicable scans every 8 weeks for the first year and then every 12 weeks. Subjects in Group 3 will undergo a PET/CT if available instead of a CT scan alone at week 16.

A subject who does not show evidence of disease progression by clinical assessment or by CT/MRI or applicable scan may continue receiving GS-5829 once daily until disease progression (clinical or radiographic), unacceptable toxicity, withdrawal of consent, or other reasons specified in Section 3.4.

For subjects in Group 2, a radionuclide bone scan (whole body) is also required at screening and then as clinically indicated or to confirm a complete response.

Study drug dosing will continue in the absence of disease progression or toxicity warranting discontinuation of therapy.

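### The fixed 21-dose count for DLT evaluability in Protocol 6.6 was not adapted to the reduced schedules allowed at Group 3 Dose Level -1, can be read two ways, and differs from Section 8.2.1.3

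*Protocol*

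**What the plan says.** Section 6.6 of the Protocol states that an evaluable subject "must receive at least 21 doses of GS-5829, complete all safety procedures through Day 28, or experience a DLT prior to Day 28". It replaces a subject only on withdrawal from the study, for a reason other than a DLT, before the DLT window ends.

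The default regimen is daily (Section 3.3): "Subjects who meet eligibility criteria will receive GS-5829 orally once daily".

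Section 3.2 provides that if 2 or more of the first 6 Group 3 subjects have a DLT, "then an additional 6 subjects will be enrolled at a lower dose level, or at an alternative dosing schedule", one that "decreases the total amount of GS-5829 administered over a 28-day period to at least 25% less than the previous cohort". The example given is "eg 14 days on and 7 days off". Table 3-3 lets this cohort open about 28 further places, under the condition "If no DLT in 6 subjects at this dose level".

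Section 8.2.1.3 defines the DLT-Evaluable Analysis Set, on which the MTD is determined. It asks for all treatment and safety procedures to be completed up to Day 29, or a DLT before Day 29. It contains no dose count.

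The SAP has no DLT-evaluable set among its analysis sets (SAP 3.1) and plans only a listing of DLTs (SAP 7.1.7.1).

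**The concern.** A fixed count of 21 suits a 28-dose schedule. The protocol also allows schedules on which 21 is the most a subject can receive, so the evaluability floor becomes the ceiling. A DLT makes a subject evaluable whatever the dose count, so any exclusion through that count removes DLT-free subjects only. The DLT rate among evaluable subjects can then move only upward.

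The sentence in 6.6 also does not settle whether doses and procedures are both required or whether either is enough, and 8.2.1.3 uses another criterion and another day. What is at stake is who counts as a DLT-free subject when Dose Level -1 is judged safe enough to expand.

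**Working it through.** **1. The dose ceiling.** Daily dosing gives 28 doses in 28 days (Section 3.3). A cut of at least 25% at the same daily dose leaves at most 0.75 × 28 = 21 doses. The protocol's example runs Days 1–14 on, 15–21 off and 22–28 on: 14 + 7 = 21 doses, and 1 − 21/28 = 25.0%. The example therefore meets the protocol's own reduction requirement exactly.

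**2. Slack against the 21-dose floor.** Daily dosing: 28 − 21 = 7 missed doses allowed. 14 on/7 off: 21 − 21 = 0. Sparser schedules cannot reach the floor: 5 on/2 off gives 20 doses, and 7 on/7 off gives 14. A lower strength taken daily still gives 28 and is unaffected.

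**3. Strict reading of 6.6 (21 doses and safety procedures, or a DLT).** Neither per-dose adherence *a* nor the true DLT rate *p* is in the documents, so both are assumed. Doses are treated as independent of each other, and adherence as independent of DLT.

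- Evaluable share of DLT-free subjects on 14/7: e = a^21.
- DLT rate among evaluable subjects: p / (p + (1 − p)e), with p = 0.15.

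| a | e on 14/7 | P(at least 21 of 28 daily doses) | DLT rate among evaluable, 14/7 |
|---|---|---|---|
| 1.00 | 1.000 | 1.000 | 15% |
| 0.99 | 0.810 | above 0.999 | 0.15/(0.15 + 0.85 × 0.810) = 18% |
| 0.97 | 0.527 | above 0.999 | 0.15/(0.15 + 0.85 × 0.527) = 25% |
| 0.95 | 0.341 | above 0.999 | 0.15/(0.15 + 0.85 × 0.341) = 34% |

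The share e falls below one half only if a < 0.5^(1/21) = 0.9675.

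**4. Literal reading of 6.6 (any one of three).** The dose count excludes nobody. But a subject with very few doses who attends the safety visits through Day 28 then counts as DLT-free, and one with 21 doses counts without the remaining procedures. The rule sets no minimum exposure, and under-exposed subjects would pull the DLT rate down.

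**5. The two sections side by side.** Section 6.6 uses a 21-dose count and Day 28. Section 8.2.1.3 uses all treatment and Day 29. If all treatment means every scheduled dose, 8.2.1.3 is stricter than 6.6. If it means only staying on treatment, it is looser. The text does not say.

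**6. Holds among the first 6 Group 3 subjects (Table 6-2).** Take a hold of 1 to 7 days that is not a DLT, starting on Day h and followed by 14 on/7 off. For h = 8 or later, at least (h − 1) + (22 − h) = 21 doses remain possible. For a hold starting on Day 4 the total is 17 to 20. Only holds starting in about the first week, with resumption on an intermittent schedule, fall below 21.

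**The case against.** A reader might infer that most DLT-free subjects on the alternative schedule cannot be scored, and that the DLT rate is therefore inflated. The documents do not support this. Twenty-one doses satisfy a floor of 21, so a fully adherent subject on the only schedule the protocol names is evaluable under either reading. A majority is lost only under the strict reading together with adherence below 96.75%, which is an assumption, or with a sparser schedule that the protocol permits but does not name. Section 5.3 also lets a late dose be taken up to 8 hours after its time, which limits missed doses.

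A reader might also infer that the expansion decision itself shifts. At a true rate of 15% and 97% adherence, the chance of 2 or more DLTs in 6 would go from 0.22 to 0.47, and of none in 6 from 0.38 to 0.18. That requires refilling until six evaluable subjects have accrued. Section 6.6 replaces only subjects withdrawn from the study, and the rule for the first six in Section 3.2 counts how many "of these 6 subjects reports a DLT within this 28 day safety period". Without refilling, the number of DLTs among the six is unchanged and the figures stay at 0.22 and 0.38. The safety review team also decides on all relevant data.

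The scope is narrow: Dose Level -1 arises only after 2 or more DLTs in the first six, it may be a lower daily dose instead, and intermittent resumption under Table 6-2 is often optional.

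All of this stands, and it limits the point to a conditional one. It does not remove it. The literal reading, which avoids the exclusions, leaves no exposure requirement. Section 8.2.1.3 does not resolve the matter, because it conflicts with 6.6 on both criterion and day.

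**Conclusion.** The evaluability rule needs rewriting whichever way it is read. Under the strict reading it allows no missed dose on 14 on/7 off and cannot be met on a sparser same-dose schedule. Under the literal reading it requires no minimum exposure. It also disagrees with the definition used for the MTD.

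The upward shift in the DLT rate among evaluable subjects is conditional on the strict reading and on assumed adherence. At an assumed true rate of 15% it runs from nothing at full adherence to about 19 percentage points (34% against 15%) at 95%. Neither selective exclusion nor a changed expansion decision is established. The SAP's design section does not describe Group 3, so the documents do not show whether Dose Level -1 was ever used. This should be corrected, but it does not undermine the daily-dosing cohorts.

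**What to change.** Use one definition in both 6.6 and 8.2.1.3. A subject is evaluable if he or she (a) received at least 75% of the doses planned for the assigned schedule in the DLT window **and** completed the safety procedures through one stated day, the same in both sections, **or** (b) had a DLT in the window.

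Seventy-five percent keeps 21 of 28 on daily dosing. On 14 on/7 off it gives 0.75 × 21 = 15.75, so 16 of 21, which allows 5 missed doses and is met with probability above 0.999 at 95% per-dose adherence.

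Add two statements: doses withheld for GS-5829-related toxicity do not make a subject non-evaluable, and non-evaluable subjects are replaced. The second should not be added without the new floor, because replacement under a fixed count of 21 is what would produce the shift from 0.22 to 0.47.

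The cost is a few sentences in two sections. Cohorts on 28 daily doses keep their present floor, and no dose, schedule or treatment rule changes. While editing, reconcile the Group 3 expansion condition as well: the text of Section 3.2 allows at most 1 DLT in the first 6, while Table 3-3 requires none.

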6.7. Dose Interruption and Reduction

The following are the guidelines for dose interruption and/or reduction. If an AE is attributed to study drug, the investigator's discretion will be used to determine if the drug not attributed to the AE will be withheld based on the investigator's assessment of risk-benefit of withholding the study drug.

6.7.1. GS-5829

For subjects without lymphoma, if at any time in the study a subject experiences a toxicity consistent with a Grade 4 DLT (see Section 3.2 for the definition of a DLT), GS-5829 treatment will be discontinued permanently, with the exception of Grade 4 neutropenia or thrombocytopenia. If a subject experiences Grade 4 neutropenia or thrombocytopenia or any other < Grade 4 toxicity consistent with a DLT (per Section 3.2), dosing with GS-5829 will be postponed until the toxicity is resolved to Grade 0 or 1 (as defined by the CTCAE, version 4.03) or returns to the subject's baseline value. If the toxicity resolves to Grade 0 or 1 or returns to the subject's baseline value within 28 days from the start of the event, the subject may resume dosing of GS-5829 at a dose that is at least one dose level lower after discussion with the Gilead Medical Monitor.

For subjects with lymphoma, if the toxicity is neutropenia or thrombocytopenia consistent with the definition of a DLT, the dose may be resumed at either one lower dose level, or the same dose with an alternative dosing schedule, which decreases the total amount of GS-5829 administered over a 28 day period to at least 25% less than the previous cohort (eg 14 days on and 7 days off). If the subject experiences a recurrence of a non-hematologic toxicity meeting criteria for DLT after restarting study drug at a lower dose or if the toxicity does not resolve within 28 days, treatment with GS-5829 will be discontinued. For subjects with lymphoma, if the recurrent toxicity is hematologic a second dose decrease is allowed (lowest dose allowed 1.0 mg) in either total daily dose or by a change in schedule such that the total amount of GS-5829 administered over a 28 day period is decreased by at least 25% after discussion with the Gilead Medical Monitor.

Table 6-2. Dose Reduction of GS-5829

NCI CTCAE Grade	Recommendation	
	Group 1 and 2: Non-lymphoma GS-5829	Group 3: Lymphoma GS-5829
HEMATOLOGICAL ADVERSE EVENTS		
Neutropenia		
Grade ≤ 3 Neutropenia	Maintain current dose level and schedule.	
Grade 4 neutropenia (or occurrence of Grade ≥ 3 neutropenia (ANC < 1000/mm ³) with fever (a single temperature of > 38.3°C or a sustained temperature of ≥ 38°C for more than one hour) or infection	Hold dosing with GS-5829 until the toxicity is resolved to ≤ 1. If the toxicity resolves to ≤ 1 within 28 days, the subject may resume dosing of GS-5829 at a dose that is at least one dose level lower after discussion with the Gilead Medical Monitor. Granulocyte-colony Stimulating Factor (GCSF) is allowed	Hold dosing with GS-5829 until the toxicity is resolved to ≤ 1. If the toxicity resolves to ≤ 1 within 4 days, the subject may resume dosing of GS-5829 at the same dose or a dose lower. If recovery to grade ≤ 1 takes > 4 days, but within 28 days, then the subject may resume dosing of GS-5829 at a dose that is at least one dose level lower after discussion with the Gilead Medical Monitor. GCSF is allowed during dose interruption, but is not to be administered on the same day as GS-5829
Thrombocytopenia		
Grade ≤ 2 Thrombocytopenia	Maintain current dose level and schedule.	
Grade 3 Thrombocytopenia	Hold dosing with GS-5829 until the toxicity is resolved to ≤ 1. If the toxicity resolves to ≤ 1 within 28 days, the subject may resume dosing of GS-5829 at a dose that is at least one dose level lower after discussion with the Gilead Medical Monitor	Hold dosing with GS-5829 until the toxicity is resolved to ≤ 1. If the toxicity resolves within 7 days, the subject may either resume at the same dose or a dose with is one level lower or at an intermittent dosing schedule. If the toxicity takes > 7 days to resolve to ≤ Grade 1, then the drug must be resumed at a lower dose or an intermittent dosing schedule after discussion with the Gilead Medical Monitor
Grade 4 Thrombocytopenia	Hold dosing with GS-5829 until the toxicity is resolved to ≤ 1. If the toxicity resolves to ≤ 1 within 28 days, the subject may resume dosing of GS-5829 at a dose that is at least one dose level lower after discussion with the Gilead Medical Monitor. If it takes > 28 days, then GS-5829 will be permanently discontinued	Hold dosing with GS-5829 until the toxicity is resolved to ≤ 1 at which time the subject may either resume at a dose with is one level lower, or at intermittent dosing schedule (at least 25% less GS-5829 in a 28 day dosing period) after discussion with the Gilead Medical Monitor.

NCI CTCAE Grade	Recommendation	
	Group 1 and 2: Non-lymphoma GS-5829	Group 3: Lymphoma GS-5829
NON-HEMATOLOGICAL ADVERSE EVENTS		
Hepatic Adverse Events (elevations in ALT, AST or bilirubin)		
Grade 1 (ALT/AST \leq 3xULN) (Bilirubin \leq 1.5xULN)	Maintain current dose level and schedule.	
Grade 2 (ALT/AST > 3-5xULN) (Bilirubin > 1.5 - \leq 3xULN)	Maintain current dose level and schedule. Monitor ALT, AST, ALP, and bilirubin at least 1x per week.	
Grade 3	Hold dosing until \leq grade 2. Permanently discontinue if any Grade 3 or Grade 4 elevation in AST or ALT associated with a Grade 2 elevation in bilirubin	
Grade 4	Permanently discontinue GS-5829	
Non hepatic, non-hematologic adverse events		
Grade \leq 2	No change in dosing required. Dosing may be interrupted until Grade \leq 1 or baseline	
Grade 3	Hold dosing until \leq grade 1 and decrease dose by at least one dose level and or by a change in schedule which decreases total GS-5829 administered over a 28 day dosing period	
Grade 4	Permanently discontinue GS-5829	

If the subject was not receiving GS-5829 at the time disease progression was documented (eg, due to reversible toxicity), after discussion with the Gilead Sciences Medical Monitor, GS-5829 may be re-started if the criteria for resuming treatment as described in Section 6.7.1 are met and the Investigator feels it is in the subject's best interest to do so.

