- Grade ≥ 3 thrombocytopenia ($< 50,000/\text{mm}^3$ to $25,000/\text{mm}^3$ which persists for > 7 days upon interruption of GS-5829

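### Table 6-2 sets no time limit on restarting GS-5829 after Group 3 thrombocytopenia, although the Section 6.7.1 text, on its natural reading, stops treatment at 28 days

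*Protocol*

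**What the plan says.** **Text of Protocol Section 6.7.1, lymphoma paragraph.** "For subjects with lymphoma, if the toxicity is neutropenia or thrombocytopenia consistent with the definition of a DLT, the dose may be resumed" in one of two ways: one level lower, or the same dose on a schedule that cuts the 28-day total by at least a quarter. The next sentence ends treatment on either of two grounds: a DLT-level non-hematologic toxicity that recurs after a restart at a lower dose, or a toxicity that has not resolved in 28 days. The sentence after that allows lymphoma subjects a second reduction for recurrent hematologic toxicity.

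**Table 6-2, Group 3 column.**
- Grade 4 neutropenia (or Grade 3 and above with fever or infection): on recovery to Grade 1 or better "within 4 days, the subject may resume dosing of GS-5829 at the same dose or a dose lower". Slower recoveries have one option, at least one level lower, under the condition "If recovery to grade ≤ 1 takes > 4 days, but within 28 days".
- Grade 3 thrombocytopenia: if resolved within 7 days, the same dose, one level lower or an intermittent schedule. Beyond 7 days, the drug has to be restarted at a lower dose or intermittently. No upper time limit is given.
- Grade 4 thrombocytopenia: once resolved, one level lower or an intermittent schedule. No upper time limit is given.

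**DLT definitions, Protocol Section 3.2.** The main list opens "A DLT in Group 1 or 2 is a toxicity defined below considered possibly related to GS-5829". The Group 3 list opens "For the first 6 subjects enrolled in the aggressive lymphoma group (Group 3), a modification of the DLT assessment for hematologic toxicity will be". On the Group 3 list the hematologic DLTs are Grade 4 neutropenia "which persist for > 3 days upon interruption of GS-5829", Grade 4 thrombocytopenia of any duration, and Grade 3 thrombocytopenia "which persists for > 7 days upon interruption of GS-5829".

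**The concern.** Text and table sit in the same section and answer the same question: may this subject restart, and at what dose? For slow-recovering thrombocytopenia in Group 3 they appear to give different answers. Section 1.5 already records a Grade 3 thrombocytopenia DLT at 3 mg, so the event is a realistic one. At stake is whether a subject with more than 28 days of unresolved thrombocytopenia comes off the drug or goes back on it. A smaller question is whether a subject with a neutropenia DLT can restart with no reduction.

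**Working it through.** **1. Which hold cells carry a 28-day limit.**

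| Event | Groups 1 and 2, non-lymphoma | Group 3, lymphoma |
|---|---|---|
| Grade 4 or febrile neutropenia | yes | yes |
| Grade 3 thrombocytopenia | yes | no |
| Grade 4 thrombocytopenia | yes, with explicit permanent discontinuation | no |

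Four of six cells have the limit. Both exceptions are Group 3 thrombocytopenia.

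**2. Those two cells against the text.** In the lymphoma paragraph the toxicity introduced at the start is neutropenia or thrombocytopenia at DLT level, so the 28-day stop most naturally refers back to it.
- Grade 4 thrombocytopenia is a DLT at any duration. If it resolves after day 28, the text discontinues and the table allows a restart.
- Grade 3 thrombocytopenia is a Group 3 DLT when Grade 3 itself lasts more than 7 days. The table branch is entered when recovery to Grade 1 takes more than 7 days, which is a slightly wider set. For those who are DLTs and resolve after day 28, the text discontinues and the table requires a restart.

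**3. The same-dose branches.**
- Platelets: recovery to Grade 1 within 7 days means Grade 3 cannot have lasted more than 7 days. On the Group 3 list this is not a DLT, so there is no conflict.
- Neutropenia: the DLT clock counts time at Grade 4 (ANC below 500/mm³) and the table clock counts time to Grade 1 or better. Both conditions hold only if Grade 4 lasts more than 3 days and full recovery comes by day 4, a window of at most 4 − 3 = 1 day. In that time the ANC must rise from below 500/mm³, past 1000/mm³ (the Grade 3 bound in Section 3.2), and through Grade 2. Growth factor during the interruption makes this conceivable. Scheduled counts in Appendix 2 fall on Cycle 1 Days 1, 4, 8, 11, 15 and 22, then Cycle 2 Day 1 (day 29) and every two weeks. The gaps are 3, 4, 3, 4, 7 and 7 days, then 14, so the window would usually show only on unscheduled counts.

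**4. The schedule option missing from the neutropenia cell.** The plan's example of 14 days on and 7 off gives 14 + 7 = 21 dosing days in the first 28: 1 − 21/28 = 25% less, as the plan states. In the long run it is 1 − 14/21 = 33.3% less. One level lower gives:

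| Step (mg) | Reduction |
|---|---|
| 12 to 9 | 25.0% |
| 9 to 6 | 33.3% |
| 6 to 4 | 33.3% |
| 4 to 3 | 25.0% |
| 3 to 2 | 33.3% |
| 2 to 1.4 | 30.0% |

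The two options reduce exposure by similar amounts, so the omission matters little.

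**5. Group 1 lymphoma.** Section 4.2, criterion 2, admits lymphoma of any subtype to Group 1. One column is headed for non-lymphoma subjects in Groups 1 and 2 and the other for Group 3, so neither fits. The 6.7.1 lymphoma text has no group restriction and does apply.

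**The case against.** The best defence is that the table is a summary. It does not repeat every rule in the text: the Grade 3 hepatic and Grade 3 non-hepatic cells also lack a 28-day limit, although the text's stop plainly reaches non-hematologic toxicity. Section 6.7 calls the rules guidelines and the table is headed as recommendations. Both Group 3 thrombocytopenia cells require discussion with the Medical Monitor before these restarts, and Section 7.5 sends toxicity questions to the Monitor. The stop can also be read as non-hematologic only, because it follows a clause on non-hematologic recurrence and hematologic recurrence is handled next.

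Part of this stands. Silence in a cell is not a waiver, and a reader who infers that the table deliberately exempts lymphoma thrombocytopenia from the stop goes further than the documents do. But the Grade 3 cell is not merely silent: it directs resumption with no end date, beside a neutropenia cell that has one. If the stop is non-hematologic only, lymphoma thrombocytopenia has no limit in either place, again unlike lymphoma neutropenia. The Monitor is a real safeguard for the slow-recovery restarts, but the same-dose branches do not mention one.

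Three stronger inferences are not supported:
- **The 3-day and 4-day neutropenia cut-offs contradict each other.** They measure different things, so they need not match.
- **Later Group 3 subjects fall under the main DLT list, making the same-dose platelet branch a wide conflict.** The modified list names only the first six, and "then up to an additional 34 subjects may be enrolled to evaluate the efficacy and tolerability of GS-5829 in lymphoma". But the main list is confined to Groups 1 and 2, and the table's 7-day platelet cut-off matches the modified list. That list is the natural one for all of Group 3.
- **Group 1 lymphoma subjects have no rule, or may use the Group 3 column.** The text gives them a rule, and nothing sends a site to a column headed for another group.

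**Conclusion.** The concern holds, as a minor safety-wording defect. Two of six hematologic hold cells, both for Group 3 thrombocytopenia, allow or require a restart with no time limit, against the natural reading of the text and the other four cells. The Group 3 neutropenia cell adds an unchanged-dose overlap (0% against at least 25% less drug) of at most about one day. The missing schedule option and the column headings are drafting points.

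This rests on two assumptions. The first is that the 28-day stop covers hematologic toxicity; if it does not, the defect is a missing limit rather than a conflict. The second is that the modified list replaces the main hematologic list in Group 3. Section 3.2 does not say whether febrile neutropenia remains a DLT there. If it does, the unchanged-dose overlap would cover any such event recovering within 4 days.

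No DLT count, maximum tolerated dose or study conclusion changes. SAP Section 1.3 reports completion with 33 subjects, and SAP Section 1.2 describes only Groups 1 and 2. The documents therefore do not show that any Group 3 subject met these rules, and the correction mainly matters for any further or reused dosing under this wording.

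**What to change.** - In both Group 3 thrombocytopenia cells, allow resumption only if the toxicity resolves within 28 days, and otherwise discontinue permanently.
- In Section 6.7.1, state that the 28-day stop includes hematologic toxicity.
- Limit same-dose resumption to cytopenias that do not meet the subject's applicable Section 3.2 DLT definition: the main list for Group 1 lymphoma, the modified list for all of Group 3. Say there whether febrile neutropenia stays on the Group 3 list.
- Add the reduced-schedule option to the Group 3 neutropenia cell.
- Add a table note that Group 1 lymphoma subjects follow the 6.7.1 lymphoma text.

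Leave the 3-day and 4-day cut-offs as they are. The cost is amendment wording in Section 6.7.1 and its table, with a short clarification of which DLT list applies. No visits, tests or subjects are added.
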